4.5. Sample Size

It is estimated that in the SoC arm, we expect 7% of patients to be on combined therapy at 24 weeks. This estimate is based on published data (Koskinas et al³) using the ELIPS study cohort which included exclusively ACS patients. A slightly lower proportion of patients (5%) may be expected to be on combination therapy at 16 weeks.

To detect a meaningful difference in proportions from the SoC group of 0.05 to 0.15 in the DSS with 90% power, we require 744 patients in 24 clusters within each arm.

This calculation assumes a two-sided statistical test at the 5% significance level, ICC of 0.1 and clusters of a similar size (31 for each site).

Justification for ICC of 0.1: Based on the article by Campbell et al.⁴, it would be reasonable for a guideline implementation study within primary care to assume an ICC of the order of 0.1 for process variables and an ICC of less than 0.05 for the outcome variable. This is also in line with empirical estimates obtained from an online database with ICC reported for cluster studies that aimed to change practice.⁵ In the database we examined the hypertension guideline interventions, these varied from 0.048 to 0.064. In addition, we have to consider clustering within country; to be conservative we have assumed an ICC of 0.1.

Based on our experience working in this setting we do not expect any loss of clusters. However, drop out may occur within clusters. As data are extracted from routinely collected electronic healthcare records, we expect missing data to be low as it will only be patients who actively request data collection to stop that will have missing outcome data. Considering a conservative approach⁶ and assuming a loss to follow-up rate of 5%, we need a minimum total sample size of 1568. Considering adjusted numbers per cluster we aim to recruit 792 over 24 clusters per arm (a total sample size of 1584).

Imperial Clinical Trials Unit	ZODIAC STATISTICAL ANALYSIS PLAN – MAIN ANALYSIS	V1 17 th Jan 2024
----------------------------------	--	------------------------------

All calculations were done using PASS 2022 software⁷ and applying a method of “Tests for Two Proportions in a Cluster-Randomised Design”.

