8.4. Primary Efficacy Analysis

The primary outcome measure, the proportion of patients treated with combination therapy, or who receive escalated monotherapy, or escalated combination therapy, within 16 weeks of the index ACS (regardless of adherence at 16 weeks) will be modelled using a generalised linear mixed model. This model will use a binomial distribution, log link function and with fixed effect for country and site type (secondary/tertiary care/mixed) and a random effect for study site (as a random intercept). If there is a convergence problem with the log-binomial model, Poisson regression with robust standard errors (modified Poisson regression) will be used. The intervention effect will be reported as a Risk Ratio with a 95% confidence interval. For primary analysis hypotheses will be tested as two-sided with a significance level of 0.05.

$$\log(\pi_{ij}) = \beta_0 + \beta_1 ACSDSS_{ij} + \beta_2 COUNTRY1_{ij} + \beta_3 COUNTRY2_{ij} + \beta_4 Site\ type_{ij} + \beta_5 Site\ type_{ij} + U_j$$

Where:

Imperial Clinical Trials Unit	ZODIAC STATISTICAL ANALYSIS PLAN – MAIN ANALYSIS	V1 17 th Jan 2024
-------------------------------	--	------------------------------

- π_{ij} : probability of combination therapy for the i^{th} patient in j^{th} site
- $ACSDSS_{ij}$: dummy variable for intervention ($ACSDSS_{ij} = 0$ or 1) for patient i in j^{th} site
- $COUNTRY1_{ij}, COUNTRY2_{ij}$: dummy variable for COUNTRY ($COUNTRY_{ij} = 0$ or 1) for patient i in j^{th} site
- $Site\ type1_{ij}, Site\ type2_{ij}$: dummy variable for Site Type ($Site\ type_{ij} = 0$ or 1) for patient i in j^{th} site type
- U_j : random effect for site $j \sim N(0, \sigma_u^2)$

This model will use the modified intention-to-treat population and will include all eligible and randomised patients through use of multi-level multiple imputation. If any participants die within 16 weeks they will be excluded from this primary analysis and any similar secondary outcome analysis but will be included in the time to event outcomes (until censored). We will tabulate mortality by intervention arm.

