14.1. Primary Outcome

```
// Load the data
use "datafile.dta", clear

// Set the maximum number of iterations
set maxiter 1000

// Fit the mixed log-binomial regression model
glm outcome intervention country site_type, family(binomial) link(log) vce(cluster site)
robust

// Display the results
estimates table
```

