14.2.2. Continuous outcomes

```
// Load the data
use "datafile.dta", clear

// Fit the mixed multi-level regression model
xtmixed outcome intervention country site_type baseline || site : , covariance(unstructured)

// Display the results
estimates table
```

Imperial Clinical Trials Unit	ZODIAC STATISTICAL ANALYSIS PLAN – MAIN ANALYSIS	V1 17 th Jan 2024
----------------------------------	--	------------------------------

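### With 48 sites and no small-sample correction specified, the primary test is likely to reject a true null about 6–9% of the time, or more with the random-intercept model, instead of 5%

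*SAP*

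**What the plan says.** SAP 8.4 models the primary outcome with a log-binomial mixed model. It has fixed effects for arm, country (two dummies) and site type (two dummies), and a random intercept for site. If this does not converge, the fallback is modified Poisson regression with robust standard errors. The error rate is fixed: "For primary analysis hypotheses will be tested as two-sided with a significance level of 0.05". SAP 8.5.3 uses the same approach for the secondary binary outcomes.

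The example code in Appendix D (14.1, 14.2.3) fits a marginal GLM with a plain site-clustered variance: "family(binomial) link(log) vce(cluster site". SAP 8.5.2 fits a linear mixed model to the lipids, with the same site-level terms plus patient-level baseline LDL-C. Its code is "xtmixed outcome intervention country site_type baseline || site : , covariance(unstructured", with no degrees-of-freedom option and no choice between ML and REML. The pooling call in 14.3 supplies no complete-data degrees of freedom.

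SAP 4.5 gives the power for a rise from 5% under routine care to 15% with the DSS: "with 90% power, we require 744 patients in 24 clusters within each arm", under an "ICC of 0.1 and clusters of a similar size (31 for each site").

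None of these sections names a reference distribution, a bias-corrected cluster variance, Kenward-Roger or Satterthwaite degrees of freedom, or a permutation test.

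**The concern.** Every fixed term in the primary model is constant within a site, so the arm effect is judged against variation between 48 sites. With six parameters estimated at that level, two things go wrong under uncorrected large-sample inference. The estimated variance is biased downwards, because the fitted site-level terms absorb part of the between-site variation. The normal critical value (1.960) is also smaller than that of t(42) (2.018). Both errors make intervals too narrow and raise the false-positive rate.

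This is the trial's one primary test. A correction chosen after the data have been seen would be open to the charge that the result drove the choice.

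**Working it through.** **1. Inputs from the documents.** 48 sites, 24 per arm (4.1); strata of 3 countries by 3 site types (4.6); two-sided 5% (8.4); 5% vs 15%, ICC 0.1, 31 per site, 744 per arm (4.5).

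**2. The plan's own figures.**
- Unpooled: (1.960 + 1.282)² × (0.05×0.95 + 0.15×0.85) / 0.10² = 183.9, so 184 per arm. The pooled-variance formula gives 188.
- Design effect: 1 + (31 − 1) × 0.1 = 4. This gives 736 (unpooled) or 752 (pooled) per arm.
- 736 / 31 = 23.7, so 24 sites × 31 = 744.
- Dropout: 744 / 0.95 = 783.2, so 784 per arm and 1568 in total. 784 / 24 = 32.7, so 33 × 24 = 792 per arm and 1584 in total.

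The stated figures are therefore reproduced with a normal test. Effective n is 744 / 4 = 186 per arm, and the noncentrality is 0.10 / √(0.175 / 186) = 3.26. Power is 0.903 with z (0.898 with the pooled formula). Replacing z by t(42) in this formula alone gives 0.890.

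**3. Analytic check (balanced linear case).**
- ML variance with z: P(|t42| > 1.96 × √(42/48)) = 0.074. The interval is 1.96 × √(42/48) / 2.018 = 0.91 of its proper width, about 9% too narrow.
- Unbiased (REML-type) variance with z: P(|t42| > 1.96) = 0.057.

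**4. Simulation of the primary test under a true null.** There were 48 sites of 31 patients, randomised in permuted blocks within nine strata, with 4,000 trials per row. The null rate, the equal site-type mix and the site-effect distribution are assumed. The Monte Carlo standard error near 8% is √(0.08 × 0.92 / 4000) = 0.4 points. Entries are % rejected at nominal 5%.

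| Null rate, ICC, site effect | Clustered Poisson, z | Clustered Poisson, t(42) | Kauermann-Carroll, t(42) | Mancl-DeRouen, t(42) | Random-intercept log-binomial, z |
|---|---|---|---|---|---|
| 5%, 0.1, beta | 8.2 | 7.4 | 6.3 | 4.5 | 9.8 |
| 5%, 0.1, lognormal | 9.2 | 8.3 | 6.4 | 4.4 | 8.2 |
| 30%, 0.1, beta | 7.0 | 6.4 | 5.1 | 3.6 | 8.2 |
| 30%, 0.02, beta | 7.5 | 6.7 | 5.2 | 3.8 | 7.5 |
| 50%, 0.1, beta | 6.4 | 5.5 | 4.2 | 3.2 | 10.9 |

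In these runs the nominal 95% interval covers 90.8–93.6% of the time for clustered Poisson with z, and 89.1–92.4% for the random-intercept model with z. The clustered z interval is 8–9% narrower than the Kauermann-Carroll t(42) interval. Changing z to t(42) alone does not restore 5%; the variance needs correcting too.

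Over all scenarios run, including other site-type mixes and unequal site sizes, clustered z inference rejected about 6–9%. The random-intercept log-binomial model with z rejected 7.4–12.2%.

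**5. Direction.** In one null run, 3.7 of 8.0 percentage points of rejections favoured the DSS; in another, 4.4 of 9.3.

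**6. Lipid model under a true null.** With country and site-type dummies and 12,000 trials per scenario, ML with z rejected 7.1–7.8%, REML with z 5.4–6.2%, and REML with t(42) 4.8–5.2%. Over all lipid runs the ranges were 6.1–7.8% (ML, z) and 5.0–6.3% (REML, z).

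**7. Simulated power at 5% vs 15%, ICC 0.1 (beta / lognormal site effects).** Kauermann-Carroll with t(42): 87.2% / 88.2%. Mancl-DeRouen with t(42): 84.0% / 85.3%. Site-level summary regression with t(42): 89.9% / 91.8%.

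**The case against.** The strongest reply is that the SAP never says it will use a normal reference. It is silent, and Appendix D is only example code; it does not even fit the random-intercept model of 8.4. This stands as a limit: the error rates are conditional on default large-sample inference. But the fallback is described only as robust standard errors, and nothing in the text or code asks for anything better.

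A second reply is that the upper end of the range depends on a 5% null rate. In 4.5 that figure is the proportion on combination therapy, whereas the primary outcome in 5.2 also counts escalated monotherapy and escalated combination therapy. The null rate of the composite is unknown and could well be higher. This also stands. At 30–50% the clustered test rejects about 6–8%, which is smaller but still above 5%. If country and site type are entered as single terms, as the code literally reads, there are four parameters and the range is 5.9–8.6%.

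Third, part of the random-intercept excess above 10% comes from a misspecified or capped random effect rather than from the z reference. That is accepted.

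Four stronger readings are tempting and are not supported:
- That the error favours the DSS. The test is two-sided and the excess splits about evenly between the arms.
- That the lipid tests share the 7–10% error. Their model is not confined to site-level terms, and their error depends on ML or REML, which the SAP does not state. Baseline LDL-C does not, however, change the roughly 42 degrees of freedom for arm.
- That every site-clustered secondary test is affected. The shared-frailty Cox model in 8.5.1 was not checked.
- That power would simply become 89%. That figure only changes the critical value and ignores the corrected variance.

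**Conclusion.** The point holds for the primary analysis and for the binary secondary outcomes that share its model. Under default large-sample inference, the nominal 5% test has a true size of about 6–9% by the site-clustered route. By the random-intercept log-binomial route it is about 7–10% or more. The 95% intervals are correspondingly too narrow. For the lipids the problem is smaller: about 6–8% under ML with z and 5–6% under REML with z.

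These sizes rest on the assumed z reference, site-type mix, null event rate, site-effect distribution and lipid ICC. The 42 degrees of freedom, and the absence of any stated correction, come directly from the SAP. It should be put right before unblinding; the design itself does not need to change.

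**What to change.** - **8.4 and 8.5.3:** name a small-sample method. One option is a Kauermann-Carroll site-clustered variance for the marginal log-binomial or Poisson model, with a t reference on realised sites minus 6. In the table this gave 4.2–6.4%, so it is close to nominal but not exact at low event rates. Mancl-DeRouen is more conservative (3.2–4.5%). If the random-intercept model stays primary, state the matching degrees-of-freedom correction for it. Moving to the marginal model changes the prespecified primary model and should be recorded as such.
- **8.5.2:** specify REML with Kenward-Roger or Satterthwaite degrees of freedom.
- **14.3:** supply the complete-data degrees of freedom when pooling imputations.
- **Appendix D:** align the code with whatever is chosen.
- **4.5:** restate power for the chosen method: about 87–88% with Kauermann-Carroll and t(42), or about 84–85% with Mancl-DeRouen and t(42).

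The cost is slightly wider intervals and, with Kauermann-Carroll, a stated power two to three points below 90%. No new data, sites or patients are needed to make the change.

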4.1. Study Design

An international, multicentre, cluster randomised, parallel arm trial with a total of 48 sites randomised to Standard of Care (SoC) [24 sites] or DSS [24 sites] across 3 countries: the United Kingdom (UK), Spain and Italy. There will be 16 sites per country; 8 DSS sites; 8 SoC sites. In the event of under-recruitment of sites in Italy or Spain, up to 6 replacement sites may be recruited from UK. DSS sites will receive a standardised period of training prior to commencing patient recruitment. Patients will be followed up for a maximum of 16 weeks. As there are no defined study visits after the patient's baseline visit all outcomes will be assessed as close to 16 weeks as possible.

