We define the primary outcome as missing for anyone who does not have full 16 week follow up, unless they have met the primary outcome prior to the time they are lost to follow up. All patients will be followed up and the primary outcome data will be collected unless the participant requests to withdraw from data collection. Missing data will be examined and quantified; this will include the time of withdrawal and tabulation for reasons for non-completion of study by country, site, and arms. Patterns of missingness and relationship between variables and outcome will be explored. The proportion of clusters (sites) with a missing individual outcome will be calculated and reported as the number of entire clusters with a missing outcome divided by the number of clusters randomised.

As mentioned in Section 4.8, some patients may have data reported at 24 weeks only. These data may be used, where appropriate, to derive or impute the LLT medication status at 16 weeks.

Although mixed models are valid under the missing at random (MAR) assumption, we will use the multilevel multiple imputation (MMI) method to impute values for individuals who have missing outcome data. Missing data can be related to the cluster level or at patient level. We define level 1 variables as those relating to the patient as X and Y and Z, and level 2 variables as those relating to the site as A and B.

Using the *JOMO package* in R with missing outcome data we can use an imputation model which is the same as the analysis model. The JOMO package allows imputation on a mix of multilevel continuous and categorical data.¹⁵ This method uses Markov chain Monte Carlo (MCMC) methods to impute missing values. We will run N imputations and combine the estimates using the mitools package. We will impute N datasets based on the percentage of participants with incomplete outcomes, where N is rounded to the nearest 10. A minimum of 5 imputation datasets will be used. We will include at patient level, intervention, outcome,

Imperial Clinical Trials Unit	ZODIAC STATISTICAL ANALYSIS PLAN – MAIN ANALYSIS	V1 17 th Jan 2024
-------------------------------	--	------------------------------

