age, sex, and comorbidities (diabetes, time since first CV diagnosis) and at site level, type of site and country in the imputation model. We do not anticipate cluster-level variables to be missing. The appropriateness of the assumption of approximate normality of the random effect of this model will be assessed graphically.

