8.8. Subgroup Analysis (of Primary Outcome)

Subgroup analysis will follow the same analysis of the primary outcome with the addition of an interaction term between the treatment and the subgroup analysis variables. These will be summarised by forest plots.

The variables investigated in the subgroup analyses are (at patient level):

- gender (men vs women)
- age (below vs above or equal to median age)
- diabetes (yes vs no)
- LLT naïve (yes vs no)
- patients experiencing one or more CV event in the 2 years prior to admission

Below is an example model for an interaction between intervention and gender added.

$$\log(\pi_{ij}) = \beta_0 + \beta_1 ACSDSS_{ij} + \beta_2 COUNTRY1_{ij} + \beta_3 COUNTRY2_{ij} + \beta_4 Site\ type_{ij} + \beta_5 Site\ type_{ij} + \beta_6 Gender_{ij} + \beta_7 ACSDSS_{ij} * Gender + U_j$$

Where:

- π_{ij} : probability of combination therapy for the i^{th} patient in j^{th} site
- $ACSDSS_{ij}$: dummy variable for intervention ($ACSDSS_{ij} = 0$ or 1) for patient i in j^{th} site
- $COUNTRY1_{ij}, COUNTRY2_{ij}$: dummy variable for COUNTRY ($COUNTRY_{ij} = 0$ or 1) for patient i in j^{th} site
- $Site\ type1_{ij}, Site\ type2_{ij}$: dummy variable for Site Type ($Site\ type_{ij} = 0$ or 1) for patient i in j^{th} site type
- U_j : random effect for site $j \sim N(0, \sigma_u^2)$
- $Gender_{ij}$: dummy variable for gender of patient i in j^{th} site

Subgroup analyses at cluster level by site type is not planned as the number of sites is anticipated to be small for some strata.

Imperial Clinical Trials Unit	ZODIAC STATISTICAL ANALYSIS PLAN – MAIN ANALYSIS	V1 17 th Jan 2024
-------------------------------	--	------------------------------

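### The listed imputation model has no treatment-by-subgroup terms and omits two of the five subgroup variables, so subgroup interactions tested on the imputed outcomes are generally diluted by roughly the missing fraction

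*SAP*

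**What the plan says.** SAP section 8.4 runs the primary analysis on the modified ITT population, with missing outcomes filled in by multilevel multiple imputation (jomo). On the form of the imputation model it says that "we can use an imputation model which is the same as the analysis model". It then lists the patient-level and site-level variables: intervention, outcome, "age, sex, and comorbidities (diabetes, time since first CV diagnosis) and at site level, type of site and country in the imputation model". No product terms are named. The example code in 14.3 puts intervention and two placeholder covariates side by side in a single call covering both arms.

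Section 8.8 states: "Subgroup analysis will follow the same analysis of the primary outcome with the addition of an interaction term". The five subgroup variables are gender, age split at its median, diabetes, LLT-naïve status, and one or more CV events in the 2 years before admission. The last two are not in the imputation list. No separate imputation is described for 8.8.

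Section 8.10 plans a complete-case analysis of the primary outcome. It does not mention one for the interactions.

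**The concern.** An imputation model should contain the terms that the analysis will test. Here a patient with a missing outcome is given one drawn as if the DSS effect were the same in both levels of the subgroup (on the imputation scale), or, for the two unlisted variables, as if the subgroup had no bearing on the outcome beyond what correlated covariates carry. The interaction model is then fitted to a mixture of real and such drawn outcomes. The subgroup estimates and the forest plot would look more alike than they should, increasingly so as more outcomes are missing.

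The absence of LLT-naïve status stands out because the outcome rule depends on it. Under section 5.2, a naïve patient started on a single drug meets the outcome only after a later step up, whereas a patient already on LLT can meet it between admission and discharge.

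**Working it through.** **1. The missing fraction the plan works with.** Section 4.5 gives "To detect a meaningful difference in proportions from the SoC group of 0.05 to 0.15 in the DSS with 90% power", and "This calculation assumes a two-sided statistical test at the 5% significance level, ICC of 0.1 and clusters of a similar size" (31 per site).
- Individually randomised: (1.960 + 1.282)² × (0.05×0.95 + 0.15×0.85) / 0.10² = 10.507 × 0.175 / 0.01 = 183.9 per arm.
- Design effect: 1 + 30 × 0.1 = 4, so 735.5 per arm. Then 735.5/31 = 23.7, i.e. 24 sites, and 24 × 31 = 744, matching "we require 744 patients in 24 clusters within each arm".
- Loss: 744/0.95 = 783.2, i.e. 784 per arm and 1568 in total, matching "assuming a loss to follow-up rate of 5%, we need a minimum total sample size of 1568". Per site 31/0.95 = 32.6, i.e. 33, giving 792 per arm and 1584.

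The plan's figures reproduce, and the planning value for the missing fraction is f = 0.05. The SAP gives no figure for the dilution itself.

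**2. Formula.** With outcomes missing completely at random, the risk in each arm-by-subgroup cell after imputation is

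completed risk = (1 − f) × true risk + f × imputed risk.

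The interaction is the log of the ratio of the two risk ratios, since 8.4 uses a log link. For an unlisted subgroup variable the imputed risk is the arm average. For a listed one it is the fit of a probit model with main effects only; I assume jomo imputes a binary outcome through an underlying normal variable. The documents give no subgroup rates, so those below are assumptions.

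**3. One case by hand.** SoC 5% in both subgroups, DSS 10% and 20%, equal halves. True log interaction: ln(0.20/0.10) − ln(0.05/0.05) = 0.693.
- Unlisted variable: the DSS average is 15%. The DSS cells become 0.95×0.10 + 0.05×0.15 = 0.1025 and 0.95×0.20 + 0.05×0.15 = 0.1975; SoC stays at 0.05. Interaction ln(0.1975/0.1025) = 0.656, a loss of 5.4%.
- Listed variable: the additive probit fit gives 3.61% and 6.52% (SoC), 11.66% and 18.22% (DSS). The completed cells are 0.0493, 0.0508, 0.1008 and 0.1991. Interaction 0.651, a loss of 6.0%, or 0.04 on 0.69.

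**4. Other assumed rates, f = 0.05, equal halves unless stated.**

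| SoC risks | DSS risks | Loss, listed | Loss, unlisted |
|---|---|---|---|
| 5/5 | 10/20 | 6.0% | 5.4% |
| 30/30 | 40/50 | 5.8% | 5.0% |
| 20/40 | 40/50 | 3.8% | 5.5% |
| 20/40 | 40/50 (25% subgroup) | 3.5% | 4.4% |
| 3/7 | 6/24 | 7.9% | 8.2% |

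Across all rates tried, the loss is 3.5% to 7.9% for listed and 4.4% to 8.2% for unlisted variables. At f = 0.20 it is 14% to 32% and 18% to 29%. With 3/7 against 9/21 the risk ratio is 3 in both subgroups, yet the additive probit model produces a log interaction of −0.012 at f = 0.05, because the imputation and the test use different scales.

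**5. Simulation with clustering.** 48 sites of 33, latent ICC 0.1, six imputations, modified Poisson with site-robust errors, 400 runs per setting, single-level probit imputation standing in for jomo, outcomes missing completely at random. The ratio is the mean interaction relative to full data.

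| Rates | Missing | Additive imputation: ratio, power | With product term: ratio, power |
|---|---|---|---|
| 5/5 vs 10/20 | 5% | 0.943, 45.2% | 1.005, 48.8% |
| 30/30 vs 36/54 | 5% | 0.944, 79.8% | 1.001, 83.2% |
| 5/5 vs 10/20 | 20% | 0.766, 23% | 1.011, 42% |
| 30/30 vs 36/54 | 20% | 0.748, 53% | 0.986, 74.5% |

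When only patients who had not yet met the outcome could go missing (nominal 5%, actual 4.1% to 4.8%), the loss was about 6%. Complete-case interactions stayed within 1% of full data at the 5% settings.

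**The case against.** The SAP lists variables, not functional form, and the code is labelled as an example with placeholder names. Since 8.4 allows the imputation model to equal the analysis model, one could read the imputation as following whichever model is fitted. That reading is possible, but nothing in 8.4, 8.8 or 14.3 states it, and it would not by itself settle how the two unlisted variables enter. The gap in specification stands.

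Missing data may also be few. Section 4.5 calls its 5% conservative. Section 8.4 counts outcomes met before loss as observed and allows 24-week data to fill gaps, and 4.8 has sites search records and contact the GP first. This stands as a limit on size, although 4.8 also counts patients as lost when no record or GP reply is available, which is wider than the active requests to stop described in 4.5.

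The consequence is small at 5%. In the simulation the interaction fell by 0.041 (0.701 to 0.660) against a standard error of 0.36, about one-ninth of a standard error, in tests the trial was not sized for. That stands too.

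A reader might infer that every interaction is pulled towards the null by slightly more than the missing fraction. The calculations do not support so general a rule: some losses are below 5%, some above 1.5 times it, and a small interaction can be created where none exists.

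**Conclusion.** The point holds at low severity. Taken as listed, the imputation model leaves out the terms that 8.8 tests and two of its five variables. True interactions are then generally diluted by roughly the missing fraction: about 4% to 8% of the log interaction at the planned 5% loss, costing about 3 points of interaction power in the two settings simulated. It becomes material only if missingness is several times the planned value.

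The sizes rest on assumed subgroup rates, subgroups of 50% or 25%, outcomes missing completely at random for the tabulated figures, and a single-level probit in place of jomo. A reader might also infer that the primary risk ratio is biased. Nothing here shows that: the primary model contains no treatment-by-subgroup term.

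**What to change.** In 8.8, with matching code in 14.3, state the imputation model for the subgroup analyses. Either:
- run jomo separately in each arm, dropping the intervention term, with all five subgroup variables as covariates; sites are nested in arms, so the random site intercept is kept; or
- keep one run and add each subgroup variable and its product with intervention.

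In both, include age at its median split as well as in its present form. Report complete-case interactions beside the imputed ones. The imputation for the primary analysis may stay as planned.

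The product-term version is the one simulated above. Imputing by arm was not simulated, but it lets every covariate effect differ between arms and so contains the same correction.

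The cost is SAP wording, a few lines of code and a second imputation run. Splitting by arm also means estimating site variance from 24 rather than 48 sites in each run, with sparser site-type cells; 8.8 already expects few sites in some strata. If that proves unstable, the product-term version avoids it. The change is best made before unblinding.
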